13.4.2. Treatment State

Within each treatment study phase (i.e. Maintenance and Extension—based on assignment of study phase described in Section 13.4.1), only those assessments which occur within the ranges shown in Table 20 will be considered ‘on-treatment’ for the given phase.

Table 20 Treatment State within Study Phases

Study Phase	Treatment State	Date Range
Screen	Pre-treatment	All assessments/events within phase
Maintenance	On-treatment	Current ART arm: Date \leq Maintenance Current ART Stop Date + 1
		IM Q4W arm: Date \leq max(Date of Last Q4W IM Dose + 35, Last Oral dose Date + 1);
	Post-treatment	Current ART arm: Date $>$ Current ART Stop Date + 1
		IM Q4W arm: Date $>$ max(Date of Last Q4W IM Dose + 35, Last Oral dose Date + 1)
Extension	On-treatment	Date \leq max(Date of Last Q4W IM Dose + 35, Last Oral dose Date + 1)
	Post-treatment	Date $>$ Date of Last Q4W IM Dose + 35, Last Oral dose Date + 1)
Long-Term Follow-up	On-treatment	Date \leq min(LTFU ART start date, max(Last Injection Date + 35, Last Oral dose Date + 1))
	Post-treatment	Date $>$ min(LTFU ART start date, max(Last Injection Date + 35, Last Oral dose Date + 1))

Note1: Treatment State is determined after data has been assigned to the study phases as defined in Section 13.4.1

Note2: Last Q4W IM / last oral dose/ Maintenance Current ART Stop Date is only applied to subjects who permanently discontinue from study treatment

Note3: Date = Assessment/Start Date.

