- This calculation will not be performed for subjects who have indicated current or past myocardial infarction conditions on the eCRF. These subjects will not be included in summary statistics of risk, but will be counted in the highest category of risk in the summary by category.

Extent of Exposure

- Exposure to CAB+RPV (oral lead-in) and CAB LA+RPV LA will be calculated from the IP eCRF pages. Exposure to Current ART will be calculated from the CONART eCRF pages.

Q4W IM arm:

- For Maintenance Phase:
 - Exposure to CAB + RPV (oral lead-in) = IP (oral lead-in) stop date- IP (oral lead-in) start date +1
 - Exposure to CAB LA + RPV LA = Number of IP injections received during Maintenance Phase
 - Overall exposure to IP = min [Date of nominal Week 52 visit, max(Date of last IP injection +35, date of last oral CAB/RPV)] - Oral lead-in CAB/RPV Start Date +1
- For Maintenance + Extension Phase
 - Exposure to CAB LA + RPV LA = Number of IP injections received during Maintenance Phase + Extension Phase
 - Overall Exposure to IP = (Date of last IP injection +35, - Oral CAB/RPV Start Date +1

Current ART arm

- For Maintenance Phase:
 - If a subject continues to Extension phase
Exposure = (IP Start Date at extension phase – 1) – Day 1 DOV + 1
 - If a subject discontinues prior to Nominal Week 52,
Exposure = Min (Current ART stop date, withdrawal date) – Day 1 DOV + 1
 - If a subject chooses to complete the study participation at Nominal Week 52 and not to continue to Extension phase, then
Exposure=completion date – Day 1 DOV +1

Current ART stop date is the last permanently stop date among all ARTs taken during Maintenance phase.

- For Extension Phase (Extension Switch Population only):
 - Exposure to CAB + RPV (oral lead-in) = IP (oral lead-in) stop date- IP (oral lead-in) start date +1
 - Exposure to CAB LA+ RPV LA = Number of IP injections received during Extension Phase
 - Overall exposure to IP = max(Date of last IP injection+35, date of last oral CAP/RPV) - Oral CAB/RPV lead-in Start Date +1
- Duration of dosing in subject years will be calculated as the sum of subject duration of dosing in days (across all subjects)/365.25
- Subjects who were randomised to CAB LA+RPV LA but did not report a IP start date will be categorised as having zero days of exposure.
- Subjects who were randomised to Current ART but withdrew on Day1 will be categorised as having zero days of exposure.

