13.13.7. Safety Tables

Safety Tables (Displays will be for both treatment arms, unless specified)					
No.	Population	IDSL / TST ID / Example Shell	Title	Programming Notes	Deliverable [Priority]
Exposure					
3.1.	Safety	Shell TS1.1	Summary of Extent of Exposure to Investigational Product – Maintenance Phase	CS Core	WK48, 96, EOS
3.2.	Safety	Shell TS1.1	Summary of Extent of Exposure to Investigational Product – Maintenance Phase + Extension Phase (for Q4W IM arm)	CS Core (only for Q4W arm)	WK48, 96, EOS
3.3.	ESP	Shell TS1.1	Summary of Extent of Exposure to Investigational Product – Extension Phase only	CS Core (only for Current ART)	WK48, 96, EOS
3.4.	Safety	Shell TS1.2	Summary of Needle Length and Gauge for CAB Injection - Maintenance Phase	(only for Q4W arm)	WK48
3.5.	Safety	Shell TS1.2	Summary of Needle Length and Gauge for RPV Injection - Maintenance Phase	(only for Q4W arm)	WK48
3.6.	Safety	Shell TS1.3	Summary of Adherence to Q4W IM Dosing Schedule (Maintenance phase)	(only for Q4W arm) please refer to Section 13.6.2 -- Adherence to CAB/RPV Injection Schedule	WK48
Adverse Events					
3.7.	Safety	AE1	Summary of All Adverse Events by System Organ Class – Maintenance Phase	CS Core (optional)	WK48
3.8.	Safety	AE5B	Summary of All Adverse Events by System Organ Class and Maximum Toxicity – Maintenance Phase	CS Core	HL, WK48
3.9.	Safety	AE5B	Summary of All Adverse Events by System Organ Class and Maximum Toxicity – Maintenance + Extension Phase	CS Core ((only for Q4W arm)	WK48, 96, EOS
3.10.	ESP	AE5B	Summary of All Adverse Events by System Organ Class and Maximum Toxicity – Extension Phase	CS Core (only for Current ART)	WK48, 96, EOS

Safety Tables (Displays will be for both treatment arms, unless specified)					
No.	Population	IDSL / TST ID / Example Shell	Title	Programming Notes	Deliverable [Priority]
3.11.	Safety	AE5B	Summary of All On-treatment Adverse Events by System Organ Class and Maximum Toxicity – Maintenance Phase	CS Core	WK48
3.12.	LTFU	AE5B	Summary of All Adverse Events by System Organ Class and Maximum Toxicity – Long-term Follow-up Phase	CS Core	WK 96, EOS
3.13.	Safety	AE5B	Summary of All Adverse Events by System Organ Class and Maximum Toxicity – Oral Lead-in Period at Maintenance phase	CS Core (for Q4W arm only)	HL, WK48
3.14.	Safety	AE3	Summary of Common Adverse Events (>=5%) by Overall Frequency – Maintenance Phase	CS Core	WK48

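### The Q4W IM Maintenance + Extension exposure formula lacks its last-oral-dose term, and neither it nor the Extension Switch formula stops at the data cut

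*SAP*

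**What the plan says.** SAP 13.6.2 (Extent of Exposure) gives three overall-exposure formulas for the same injectable regimen.

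- Q4W IM arm, Maintenance: "Overall exposure to IP = min [Date of nominal Week 52 visit, max(Date of last IP injection +35, date of last oral CAB/RPV", with the brackets then closed and the oral start date subtracted. It has an oral-dose term and an upper limit at the Week 52 visit.
- Q4W IM arm, Maintenance + Extension: "Overall Exposure to IP = (Date of last IP injection +35, - Oral CAB/RPV Start Date +1". It has no operator, no oral-dose term and no upper limit.
- Extension Switch Population: "Overall exposure to IP = max(Date of last IP injection+35, date of last oral CAP/RPV) - Oral CAB/RPV lead-in Start Date +1". It has the oral-dose term but no upper limit.

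The days are then summed: "Duration of dosing in subject years will be calculated as the sum of subject duration of dosing in days (across all subjects)/365.25". The second formula serves Table 3.2 in 13.13.7, titled "Summary of Extent of Exposure to Investigational Product – Maintenance Phase + Extension Phase (for Q4W IM arm"), in the Safety population. The third serves Table 3.3. Both tables are due at Week 48, Week 96 and end of study.

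The one rule for missing values in this arm is "Subjects who were randomised to CAB LA+RPV LA but did not report a IP start date will be categorised as having zero days of exposure". The other imputation rule in that section, for a missing discontinuation date, applies to the Current ART arm only.

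**The concern.** Two separate gaps follow from the text.

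**Missing oral term.** The Safety population (section 4) takes in anyone with at least one dose of IP. Section 13.4.1 provides explicitly for participants who withdraw before their first injection. Such a person has an oral start date but no injection date, so the Maintenance + Extension formula returns nothing. The zero-day rule does not help, because an IP start date exists. The SAP also foresees oral bridging (13.6.2 adherence categories, 13.6.5, 13.11), and bridging that outlasts the 35-day period is not counted.

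**Missing bound.** For someone still being dosed at a data cut, the last injection plus 35 days lies after the cut. The Maintenance + Extension and Extension Switch formulas count those days as exposure although they have not yet been observed.

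At stake are the reported days and subject-years on CAB + RPV. A programmer must also guess the missing argument, and different guesses give different totals.

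**Working it through.** The SAP states no exposure figure, so there is none to reproduce. The check evaluates the formulas on illustrative participants.

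**Notation.** S = oral CAB/RPV start (day 0), I = last injection, O = last oral CAB/RPV dose, C = data cut, all in days from S.

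- Maintenance: min[Week 52 visit, max(I + 35, O)] − S + 1
- Maintenance + Extension as written: I + 35 − S + 1
- Extension Switch: max(I + 35, O) − S + 1

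**Inputs.** The formulas are from 13.6.2. The 28-day injection interval is from 13.6.4 (Delay in IP Injection). N = 570 randomised 1:1 is from 2.3, so 570/2 = 285 in the Q4W arm. The number ongoing at a cut and the length of bridging are not given, so these are assumed.

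**1. Lead-in only, last oral dose on Study Day 28 (O = 27).**
- As written: I does not exist, so the value is undefined.
- Maintenance formula, using the oral date alone: 27 + 1 = 28 days.
- Extension Switch form, same treatment: 28 days.

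**2. Oral bridging after a last injection at I = 364.** As written, exposure is 364 + 35 + 1 = 400 days in every case.

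| Bridging ends | With oral term | Undercount |
|---|---|---|
| I + 28 | 400 | 0 |
| I + 35 | 400 | 0 |
| I + 56 | 364 + 56 + 1 = 421 | 21 days |
| I + 84 | 364 + 84 + 1 = 449 | 49 days |

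**3. Ongoing and on schedule at the cut.** Let g be the days from last injection to the cut, 0 to 27 under 28-day dosing. Days credited past the cut = 35 − g, which runs from 8 to 35. With cuts spread evenly over the interval the mean is (8 + 35)/2 = 21.5. Example: I = 672 and C = 672 gives 672 + 35 + 1 = 708 days as written, against 672 + 1 = 673 when bounded at the cut.

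**4. Subject-years past the cut** = number ongoing × days / 365.25.

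| Ongoing (assumed) | At 8 days | At 21.5 days | At 35 days |
|---|---|---|---|
| 100 | 2.2 | 5.9 | 9.6 |
| 200 | 4.4 | 11.8 | 19.2 |
| 285 (whole arm, upper limit) | 6.2 | 16.8 | 27.3 |

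**5. Comparison with the SAP's other rules.** The on-treatment definition for the Extension phase (Table 20) takes the later of last injection + 35 and last oral dose + 1, so it includes an oral term. The time-to-event censoring rule in Appendix 15 takes the minimum of that same quantity and other dates, among them the last contact date. Both elements missing from the exposure formula are therefore already in use elsewhere.

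**The case against.** The strongest reply is that the printed formula is a drafting fragment. The open bracket and hanging comma show that an operator and a second argument were lost, and the formulas on either side suggest what they were. On that reading the intended rule already covers lead-in-only and bridged participants. This is probably right about intent, but the text still cannot be programmed without a guess. It also does not explain the missing bound, because the Extension Switch formula is intact and has none.

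A second reply is that last injection + 35 is the SAP's standard coverage period for a long-acting dose, and that the Maintenance formula is not limited at a data cut either, only at the Week 52 visit. Both are true. The second argues for adding the bound to all three formulas.

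Several stronger readings are tempting, but the SAP does not support them:

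- **That both gaps lengthen reported exposure.** They pull in different directions. Losing lead-in-only participants raises the mean but lowers total subject-years. Uncounted bridging shortens exposure. Only the missing bound lengthens it throughout.
- **That safety rates are biased through their denominator.** The planned adverse event tables are subject incidences, and the injection-site-reaction rate is per injection visit. No exposure-adjusted event rate is planned.
- **That Table 20 Note2 contradicts the formula.** It says the last-dose date "is only applied to subjects who permanently discontinue from study treatment", but it governs treatment state, not exposure.
- **That exposure should also stop at long-term follow-up ART or at transfer to ATLAS-2M.** No exposure formula in 13.6.2 uses either date, and no cross-study exposure sum is planned. Adding these limits to Maintenance + Extension alone could give one participant less exposure in Table 3.2 than in Table 3.1.
- **That the excess can be stated as a percentage of total exposure.** The SAP gives neither the number ongoing nor the mean follow-up.

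**Conclusion.** The point holds as a minor defect in a descriptive derivation. As printed, the Maintenance + Extension formula has no value for lead-in-only participants in Table 3.2 and misses bridging beyond 35 days after the last injection. No other SAP rule repairs this. Lead-in-only participants still have a defined value in Table 3.1, so the loss is confined to the Maintenance + Extension display.

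The missing bound affects Tables 3.2 and 3.3 at the Week 48 and Week 96 cuts. The figure of 8 to 35 days per participant assumes on-schedule dosing. The totals of about 6 to 17 subject-years use the mean of 21.5 days, assume 100 to 285 ongoing participants and refer to the Q4W arm only. The end-of-study analysis follows completion by all participants (section 3), so this overhang from ongoing participants should not arise there. The primary endpoint and all efficacy analyses are untouched.

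**What to change.** For Maintenance + Extension, replace the formula with:

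min[data cut-off or last contact date, max(date of last IP injection + 35, date of last oral CAB/RPV)] − oral CAB/RPV start date + 1

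State that the last oral dose is used alone when no injection was given. Add the same bound to the Extension Switch formula and, for consistency, to the Maintenance formula alongside its Week 52 limit. Choose either the data cut-off or the last contact date once, and apply it throughout.

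The cost is a line of SAP wording and a small change to the derivations, with no new data. The downside is that reported subject-years become slightly smaller at the interim cuts.

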13.6.3. Safety

Adverse Events– DAIDS Grading

 Clinical adverse events will be graded based on the Division of AIDS Table for Grading the Severity of Adult and Paediatric Adverse Events Version 2.0, November 2014, as specified in the protocol Appendix 12.2.
Laboratory Parameters

 If a laboratory value which is expected to have a numeric value for summary purposes, has a non-detectable level reported in the database, where the numeric value is missing, but typically a character value starting with '<x' or '>x' (or indicated as less than x or greater than x in the comment field) is present, the number of significant digits in the observed values will be used to determine how much to add or subtract in order to impute the corresponding numeric value. If a character value starting with "<=x", then the numeric value will be x. 
 Example 1: 2 Significant Digits = '< x ' becomes x – 0.01 Example 2: 1 Significant Digit = '> x' or '>=x' becomes x + 0.1 Example 3: 0 Significant Digits = '< x' becomes x – 1
Estimate of Glomerular Filtration Rate (GFR)

 Chronic Kidney Disease Epidemiology Collaboration (CKD-EPI) equation [Levey, 2012] will be used by the central laboratory to provide an estimate of GFR, in mL/min per 1.73 m², as follows: $GFR = 141 \times \min\left(\frac{CRT_{mg/dL}}{\kappa}, 1\right)^\alpha \times \max\left(\frac{CRT_{mg/dL}}{\kappa}, 1\right)^{-1.209} \times 0.993^{Age} \times [1.018 \text{ if Female}] \times [1.159 \text{ if Black}]$ 
where age (in years) is at time of assessment, κ = 0.7 if female or 0.9 if male, α = -0.329 if female and -0.411 if male, min() indicates the minimum of CRT/κ or 1, max() indicates the maximum of CRT/κ or 1, and CRTmg/dL is serum creatinine concentration in mg/dL. The serum creatinine concentration in mg/dL is obtained from GSK standard units of μmol/L as CRTmg/dL =0.0113x CRTμmol/L.
 
 The CKD-EPI GFR will also be calculated using Cystatin C, as follows 133 X min(Scys/0.8, 1) ^{-0.499} X max (Scys/0.8, 1) ^{-1.328} X 0.996 ^{Age} X [0.932 if female] 
Where Scys is serum cystatin C mg/Liter, min indicates the minimum of Scr/0.8 or 1, and max indicates the maximum of Scys/0.8 or 1

Lab Toxicities – DAIDS Grading based on Version 2.0, November 2014, as specified in the protocol of Appendix 12.2

 Toxicities will be based on the Division of AIDS (DAIDS) grading system, Version 2.0, November 2014, as specified in the protocol of Appendix 12.2. Toxicity grades provided by the central laboratory do not distinguish between abnormally high or low criteria, when both are relevant for a particular parameter.

Laboratory Parameters

- When summarising toxicity grades for such parameters, they will be categorised as to whether they are above or below the midpoint of normal range.

Parameter	Below Midpoint for those \geq Grade 1	Above Midpoint for those \geq Grade 1
Fasted glucose	Hypoglycaemia	Hyperglycaemia
Sodium	Hyponatremia	Hypernatremia
Potassium	Hypokalaemia	Hyperkalaemia

National Cholesterol Education Program (NCEP) Lipid Categories

- In addition to DAIDS toxicity grades (see protocol), lipid values will be categorized according to the 2001 NCEP Adult Lipid Guidelines [Grundy, 2001]

Parameter	Value Range (mmol/L)	Value Range (mg/dL)	Category
Triglycerides	<1.70	<150	Normal
	1.70 to <2.26	150 to <200	Borderline High
	2.26 to <5.65	200 to <500	High
	\geq 5.65	\geq 500	Very High
Total Cholesterol	<5.18	<200	Desirable
	5.18 to <6.21	200 to <240	Borderline High
	\geq 6.21	\geq 240	High
HDL Cholesterol	<1.04	<40	Low
	1.04 to <1.56	40 to <60	Normal
	\geq 1.56	\geq 60	High
LDL Cholesterol	<2.59	<100	Optimal
	2.59 to <3.37	100 to <130	Near/Above Optimal
	3.37 to <4.14	130 to <160	Borderline High
	4.14 to <4.92	160 to <190	High
	\geq 4.92	\geq 190	Very High

Total Cholesterol / HDL Cholesterol Ratio

- When both total cholesterol and HDL cholesterol results are available from the same date for a subject, then the ratio will be calculated by dividing the total cholesterol result by the HDL cholesterol result. The ratio can be classified as follows:

Parameter	Value Range
Total Cholesterol / HDL Ratio	< 3.5
	3.5 to < 4.4
	4.4 to < 5
	\geq 5

Percentage change for lipids

The percentage change from baseline is calculated as:

$$\% \text{ change from baseline} = \frac{\text{value at Week 48} - \text{baseline value}}{\text{baseline value}} \times 100\%$$

Other Safety Endpoints
Columbia Suicide Severity Rating Scale (C-SSRS) (Posner, 2007)

 Missing data will not have any imputation performed (Nilsson, 2013)

13.6.4. Efficacy

Snapshot

 The Snapshot algorithm is intended to be primarily a virologic assessment of the endpoint, and as such follows a “virology first” hierarchy. ‘HIV-1 RNA <50 c/mL’ or ‘HIV-1 RNA ≥50 c/mL’ within an analysis window (see Table 11) is typically determined by the last available HIV-1 RNA measurement in that window while the subject is On-treatment in the Maintenance Phase (as assigned based on Table 20). 
 When no HIV-1 RNA data is available within a window, a subject cannot be assigned to the category of ‘HIV-1 RNA < 50 c/mL’. Depending on the reason for lack of data, the subject will be classified as a ‘HIV-1 RNA≥50’ or reported as ‘No Virologic Data at Week X’; in the latter case, the algorithm further classifies the nature of the missing data. Typically, a subject withdrawn (i) due to AE or, (ii) for another reason yet was suppressed at the time, will be counted as ‘No Virologic Data at Week X’. Should a subject withdraw for reasons other than AE and was not suppressed at the time, they will be a ‘HIV-1 RNA≥50’. For each scheduled assessment time, the Snapshot response rate for a given threshold (e.g., <50 c/mL) is defined as: $\text{Snapshot Response Rate} = \frac{\text{Number of responders in that analysis window}}{\text{Number of subjects in the analysis population}}$ 
 For each scheduled assessment time, the Snapshot ‘HIV-1 RNA≥50’ rate for a given threshold (e.g., ≥50 c/mL) is defined as: $\text{Snapshot VF Rate} = \frac{\text{Number of VFs in that analysis window}}{\text{Number of subjects in the analysis population}}$ 
 Full details of the algorithm, including the handling of special cases, are included in Section 13.11
Plasma HIV-1 RNA

 For summaries and analyses which use HIV-1 RNA level as a continuous measure, the logarithm to base 10 of the value will be used. HIV-1 RNA results may be provided as censored values, such as <40 or >9,999,999 c/mL. For the purposes of summary statistics, such values will be replaced by the next value beyond the limit of detection, e.g., 39 or 10,000,000 c/mL, respectively, for the given examples. Data listings will show the censored values as provided.
Target Detected / Target Non-Detected/Super low viral load testing

 When a measurement of plasma HIV-1 RNA is below the limit of quantification (i.e. 40 c/mL) and is qualitatively observable that will be denoted as a “Target Detected” measure, while HIV-1 RNA below the limit of quantification that is not qualitatively observable that will be denoted as “Target Not Detected”. Any measurements <40 c/mL characterised as “Target Non-Detected” or

“Target Detected” will be captured in the database.
 
 • Super low viral load will also be tested by BioMNTR lab for Viral loads below the limit of quantification at some visits (e.g. Week 48)

Treatment (TRDF) and Efficacy Related (ERDF) Discontinuation = Failure

 • The analysis of time to confirmed virologic failure (CVF) or discontinuation due to treatment related reasons (i.e., drug-related AE, intolerability of injections, protocol defined safety stopping criteria, or lack of efficacy) will censor subjects who have not met CVF criteria and are ongoing in the study, or who have discontinued for reasons other than those related to treatment. This will be the Treatment Related Discontinuation = Failure (TRDF) data. • Subjects who have not met CVF criteria and are ongoing in the study, or who have discontinued for reasons other than lack of efficacy, will be censored in the analysis of the Efficacy Related Discontinuation = Failure (ERDF) data. • Proportion of Participants without virologic (ERDF) or tolerability (TRDF) failure will be estimated using the Kaplan-Meier nonparametric method based on the time to ERDF or TRDF. The estimated proportion at Week 48 will be presented by treatment group, along with estimated difference in proportions between treatment groups and its associated two-sided 95% CI. The estimate of the standard error used to derive confidence intervals will be based on Greenwood’s formula [Kalbfleisch, 1980].

Observed Case Summary for Subjects per Viral Load Category by Visit (Maintenance Phase)


 • For each visit with scheduled viral load collection (per time and events schedule in the protocol), the Observed Case proportion is defined using available data, with no imputation for missing values. • Denominator: Number of subjects with on-treatment viral load within the analysis Snapshot visit window (e.g. Week 48 \pm6 weeks). • Numerator: Number of subjects with HIV-1 RNA <threshold (e.g. 50 c/mL) based on the last viral load assessment collected within the analysis Snapshot window (e.g. Week 48 \pm6 weeks). For Baseline, the last viral load collected prior to or equal to the date of first maintenance phase study treatment dose will be selected for determining the observed case proportion at this timepoint.

Confirmed Virologic Failure (CVF)

 • The definition of CVF is provided in the Protocol, Section 5.4.4 – Definition of Virologic Failure

HIV-1 Disease progression Stage

 • Categories: 
 ○ CDC Stage I at baseline to CDC Stage III; ○ CDC Stage II at baseline to CDC Stage III; ○ CDC Stage III at baseline to new CDC Stage III event and ○ CDC Stage I, II, III at baseline to death. 
Please refer to Protocol (Appendix 4: CDC Classification for HIV-1 Infection) for defining Stage. For the purpose of analysis, the CDC at baseline and at post-baseline during maintenance phase will be derived as below:
 
 • At Baseline, the ‘Baseline CDC stage’ for each subject was assessed by investigator and recorded in the eCRF. However, for the analysis, the Baseline CDC stage will be re-derived based on Baseline CD4+ values as well as whether any HIV-associated conditions present at baseline per the Criteria’s thresholds (Appendix 4 in Protocol). • To analyse disease progression, the most advanced post-baseline CDC stage will be

derived based on the occurrences of new AIDS-defining conditions (please refer to Appendix 4 in Protocol for the list of AIDS-defining Conditions) as well as the nadir value of post-baseline CD4+. For example,

- If a subject with CDC 'Stage I' at baseline had the lowest post-baseline CD4+ =120 cell/mm³ without new AIDS-defining conditions, then HIV disease progression for this subject would be considered as 'CDC stage I at baseline to CDC stage III'.
- If a subject with CDC 'Stage II' at baseline had the lowest post-baseline CD4+ =220 cell/mm³ AND had at least one new AIDS-defining condition, then HIV disease progression for this subject would be considered as 'CDC stage II at baseline to CDC stage III'.

Delay in IP Injection

IM dosing is expected to occur every 4 weeks from Week 4b onwards. The Delay in IP injection (days) will be calculated as below:

- Delay in IP injection(days) = Injection date - date of preceding injection – 28 days

Delay in IP injection will be grouped into: ≤1, 2-3, 4-7, >7 days.

The proportion of subjects with HIV-1 RNA ≥50 c/mL at Week 48 (Snapshot) will be summarized by last delay in IP Injection. The last delay in IP injection will be the delay in IP injection at Week 48, or the delay in last IP injection prior to Week 48 if a subject does not receive Week 48 injection (i.e. missing visit or withdrawal).

